1. AMENDMENTS FROM PREVIOUS VERSION(S)

Status of the study when amendments were made: Study is still ongoing and blinded.

Final Date: 04-Jan-2013 Version 1.0	1. This is the first SAP for protocol A0081105.	1. N/A
Amendment 1 Date: 21-Apr-2017 Version 2.0	
2. Updated to the reference of the blinded sample size formula of Friede and Kieser (2011) to apply the latest methodology with considering covariate of continuous data under Section 2.2, References, and Appendix 6.
 
From: Kieser, M. and Friede, T. (2003). Simple Procedures for Blinded Sample Size Adjustment that Do Not Affect the Type I Error Rate. Statistics in Medicine, 32: 3571-3581.
 
To: Friede, T and Kieser, M. (2011). Blinded Sample Size Recalculation for Clinical Trials with Normal Data and Baseline Adjusted Analysis. Pharmaceut. Statist., 10: 8-13.
 
3. Added the description to explain the procedure for final analysis and unblinding under Section 3.2.
 
4. Revised the analysis of pattern mixture model under Section 7, Reference, and Appendix 4.
 
5. Added to calculate odds ratio with 95% confidence interval of responder rate and added the explanation of SAS code for p-value calculation under Section 8.2.
	
2. To update the sample size re-estimation reference.
 
3. To match protocol procedure.
 
4. To replace multiple imputation analysis method consistent with A0081041 and A0081042.
 
5. To add detailed specification of the responder analysis with SAS code.


Amendment 2
 
Date: 01-Mar-2019
 
Version 3.0
	
1. Add the following equation in Section 6.1, Section 8.1, and Appendix 1 for additional presentation of percent reduction of treatment difference relative to placebo:
 $100\% \times \frac{\exp(\text{LSMean(pregabalin)}) - 1 - [\exp(\text{LSMean(placebo)}) - 1]}{\exp(\text{LSMean(placebo)}) - 1}$ 
2. Amended the seizure type for evaluation from partial seizures to PGTC seizures under Section 6.1.3.4.
 
3. Removed cognitive testing of safety endpoint under Section 6.2.
 
4. Added a sensitivity analysis with age group (5-16 years of age and 17-65 years of age) as a covariate in Section 8.1.
 
5. Added a supplemental analysis with treatment-by-age group (5-16 years of age and 17-65 years of age) interaction term in the ANCOVA model in Section 8.1.
 
6. Updated geographical region definition under Section 6.4 with consideration of enrollment by country based on SSR dataset, and updated the definition to remain consistent under Section 8.1.
 
7. Moved supplemental analysis detail from Section 7 to Section 8.
 
8. Updated a sensitivity analysis of pattern mixture model of multiple imputation under Section 8.1, Section 8.5 and Appendix 4.
 
9. Updated dependent variable of ranked ANCOVA and Wilcoxon-Mann Whitney test from “log-transformed 28 day seizure rate” to “change from baseline to double blind phase of log-transformed 28
	
1. This back transformation was requested by FDA for A0081042. It is added to be consistent with A0081042.
 
2. Correction, consistent with the protocol-specified population.
 
3. Cognitive testing was not included in the study protocol.
 
4. To differentiate results in pediatric vs adult population.
 
5. Specified in the protocol.
 
6. Based on actual enrollment.
 
7. Editorial changes.
 
8. Added more details with multiple imputation.
 
9. To be consistent with A0081042 analyses and to be able to adjust the model for any baseline seizure imbalance.
 
10. The plot is not necessary as the interaction is

--	--	--

	
day seizure rate" under Section 8.1.
 
10. Removed the possibility of forest plot to evaluate interaction by age under Section 8.1.
 
11. Updated the analysis with Poisson and negative binomial models with considering baseline seizure count as a covariate and Pearson as the scale parameter (Poisson model only) under Section 8.1, Section 8.5 and Appendix 5.
 
12. Updated the analysis of the proportion of seizure-free days for each seizure type from logistic regression to ANCOVA analysis under Section 8.3.
 
13. Clarified the definition of proportion of subjects with PGTC seizure-freedom in Section 6.1.3.3.
 
14. Added clarification regarding seizure free days and proportion of seizure free days in Section 6.1.3.1.
 
15. Clarified the definition of number of 12 week adjusted seizure free days gained in Section 6.1.3.2.
 
16. Added contingency plan in case the primary analysis model fails due to covariates of region and age strata in Section 8.1.
 
17. Added a secondary analysis based on combined European Union and US
 
18. Added clarification of responder rate
	
analytically checked by ANCOVA model
 
11. To be consistent with A0081042 analyses, to adjust for baseline seizure imbalance in the model (Pearson as the scale parameter).
 
12. To correct an error in the analysis model in the previous SAP.
 
13. To be consistent with adult PGTC seizure-freedom definition used in past pregabalin studies.
 
14. To add detailed specifications.
 
15. To add detailed specifications.
 
16. To make analysis viable in case small numbers of subjects in certain region(s) and/or age strata cause any issue with analysis model.
 
17. Based on blinded number of subjects across countries, US enrolled only 5 subjects
 
18. Make the definition of responder rate more clear

Date: 18-Mar-2019	1. Revised responder definition in Appendix I	1. To make the definition of responder rate consistent with adult

Version 4.0		study's definition.
-------------	--	---------------------

[figure not shown]
2. INTRODUCTION

Protocol A0081105 is a randomized, double-blind, parallel-group, placebo-controlled, multi-center trial in subjects 5 to 65 years of age with PGTC seizures. This study will evaluate the efficacy of 2 dose levels of pregabalin [Dose Level 1: pregabalin 5 mg/kg/day (maximum 300 mg/day) or Dose Level 2: pregabalin 10 mg/kg/day (maximum 600 mg/day), administered BID] compared with placebo.

2.1. Study Design

This study will consist of an 8-week baseline phase, a 12-week double-blind assessment phase (including a 2-week double-blind dose escalation phase and a 10-week double-blind fixed dose phase), and a 1-week double-blind taper phase. Eligible subjects will be randomly assigned to receive double-blind treatment with 1 of 2 dose levels of pregabalin or placebo. Study drug treatments are to be taken orally twice daily (BID) in equally divided doses for 12 weeks during the double-blind assessment phase and then 1 week double-blind taper. Subjects who complete the double-blind phase of this trial may be eligible for screening for a 1-year open-label pregabalin safety study.

A total sample size of 168 subjects (ie, 56 subjects per group) is needed to have been randomized, received treatment and had a baseline and post baseline efficacy assessment. Randomization will be stratified by site and subject age (Stratum 1: 5-7 years of age; Stratum 2: 8-11 years of age; Stratum 3: 12-16 years of age; Stratum 4: 17-65 years of age). Subjects in each age stratum within site will be randomized to a fixed dose of either placebo, Dose Level 1: pregabalin 5 mg/kg/day (maximum 300 mg/day) or Dose Level 2: pregabalin 10 mg/kg/day (maximum 600 mg/day) in a 1:1:1 ratio. Approximately 30% of planned enrollment (approximately 50 subjects) will be subjects <17 years of age. Every reasonable effort will be made to enroll a minimum of 12 subjects in each of the 4 age strata.

Study Design Diagram:

*Eligible subjects may be assessed for a 1-year open-label pregabalin safety study (Study A0081106) and complete end of study activities for A0081105 at Visit 10 (V10).

** Dose Level 1: 7 mg/kg/day for pediatric subjects <30 kg and 300 mg/day for subjects ≥ 17 years of age.

*** Dose Level 2: 14 mg/kg/day for pediatric subjects <30 kg and 600 mg/day for subjects ≥ 17 years of age.

Phone visits are also scheduled for Study Days 3, 10, 17, and 89 (each with a ± 3 day window).

2.2. Statistical Power and Sample Size

A total sample size estimate of 168 subjects allows for the evaluation of efficacy using the primary endpoint, $\log_e(28\text{-day seizure rate} + 1)$, for making comparisons between placebo vs. 5 mg/kg/day pregabalin (maximum 300 mg/day; Dose Level 1), and placebo vs. 10 mg/kg/day (maximum 600 mg/day; Dose Level 2) pregabalin groups for the treatment period of the study. The following sample size assumptions and corresponding power calculations are provided in Table 1 below. This sample size will also allow for a general assessment of safety and tolerability.

Table 1. Power Calculations and Sample Size Assumptions with 56 Subjects per Group for the Primary Endpoint (\log_e (28-day seizure rate + 1))

Comparison	Log Transformed Difference from Placebo	Percent Difference from Placebo	SD (log transformed 28 day seizure rate)	Power
Expected difference ¹ between 600 mg/day and placebo	-0.534	-41.4%	0.73 0.67	0.970 0.984
Expected difference ¹ between 300 mg/day and placebo	-0.358	-30.1%	0.73 0.67	0.742 0.800

¹ Expected difference is 80% of the observed difference between the specified pregabalin dose minus placebo based on a meta-analysis of Studies 1008-009, 1008-011, and 1008-034 based on the log transformed 28 day seizure rate, with 300 mg/day only in Study 1008 -034.

The primary statistical analysis will model the log transformed 28 day seizure rate, and compare each dose of pregabalin to placebo in a step-wise manner, starting with the highest dose of pregabalin. Since there is a significant dose response of pregabalin, the power to detect expected differences for each pregabalin dose relative to placebo will be different. Hence, this step-wise testing procedure will provide maximum power as well as control for multiplicity of testing at the desired 0.05 level of significance for the primary analysis.

Based on a meta-analysis of double-blind placebo controlled adult adjunctive therapy studies (Studies 1008-009, 1008-011, and 1008-034) using the log transformed 28 day seizure rate, the expected differences from placebo (ie, the difference in the observed least squares means after adjusting out the study-to-study differences and site clustering within study effects) were -0.668 (-48.7%) and -0.448 (-36.1%) for 600 mg/day (Dose Level 2) and 300 mg/day (Dose Level 1), respectively. This study is powered on 80% of these estimated treatment differences; -0.534 (-41.4%) and -0.358 (-30.1%) for 600 mg/day (Dose Level 2) and 300 mg/day (Dose Level 1), respectively.

A meta-analysis of Studies 1008-009, 1008-011, and 1008-034 was used to estimate a pooled standard deviation of 0.73 on the log transformed 28 day seizure rate scale, with a 95% confidence interval of [0.70, 0.76]. For the purposes of this study, a smaller standard deviation of 0.67 was used to assess the power and initial sample size requirements for comparing the 2 pregabalin group to placebo. The rationale for assuming the smaller SD of 0.67 is based on the Study 1008-034 data which included all three treatment groups of interest (i.e., placebo, 300 mg/day, and 600 mg/day). This study had a point estimate for the standard deviation of 0.72 and a 95% confidence interval for the standard deviation of [0.67, 0.77].

To ensure that the sample size is reasonably sufficient using an assumed pooled standard deviation of 0.67 on the \log_e scale, in order to provide at least 80% power to detect a

treatment difference of 0.358 on the log_e scale a blinded sample size re-estimation procedure (Friede and Keiser, 2011)³ based upon a residual variance of ANCOVA under the null hypothesis will be applied when approximately the first 110 subjects in total have had the opportunity to complete the study (ie, no ongoing subjects will be included in this sample size re-estimation procedure). The blinded sample size re-estimation procedure for this study will not allow for a reduction in the planned sample size of 56 subjects per group or an increase in sample size greater than 65 subjects per group (195 subjects total). This represents the sample size required to provide 80% power to detect a treatment difference of -0.358 on the log scale with a standard deviation of 0.72. The sample size also allows for operational feasibility. Details regarding the statistical methodology of the blinded sample size re-estimation procedure will be documented in Appendix 6. This blinded sample size re-estimation procedure will be conducted by a statistician who is not associated with the conduct or final analysis of the study.

There will be no penalty applied to the p-values or confidence intervals for assessing treatment difference from placebo due to this blinded sample size re-estimation procedure.

2.3. Study Objectives

Primary Objective:

- To demonstrate superior efficacy of pregabalin compared to placebo for treatment of PGTC seizures as measured by the 28 day seizure rate.*

Safety Objectives:

- To assess the safety and tolerability of pregabalin relative to placebo in pediatric and adult subjects with PGTC seizures.*

Secondary Objectives:

- To demonstrate superior efficacy of pregabalin compared to placebo for PGTC seizures as determined by responder rate.*

Exploratory Efficacy Objectives:

- To demonstrate superior efficacy of pregabalin compared to placebo as determined by seizure-free days for PGTC, myoclonic, tonic/tonic, absence, and clonic seizures.*

- *To demonstrate superior efficacy of pregabalin compared to placebo as determined by seizure-freedom of PGTC seizures over the last 28 days of the double-blind assessment phase and over the entire double-blind assessment phase. In those subjects with myoclonic, tonic/tonic, absence, or clonic seizures at baseline, seizure freedom over the last 28 days of the study and over the entire double-blind assessment phase will be summarized descriptively.*
- *To demonstrate superior efficacy of pregabalin compared to placebo as determined by the time to experience the same total number of PGTC seizures in the 12-week double-blind assessment phase that was observed during the baseline phase for each subject (referred to as 'Time to Nth Seizure'). This analysis will be reported separately from the main clinical study report.*

3. INTERIM ANALYSES, FINAL ANALYSES AND UNBLINDING

3.1. Interim Safety Analysis

In addition to the regular review of blinded safety data during the conduct of the study, as described in the "Safety Analysis" section, 2 unblinded Interim Safety Analyses (ISA) to be reviewed by an E-DMC will be conducted to further assess safety. The timing of the first ISA will be when the first one-third of the subjects enrolled (randomized) has had an opportunity to complete the study. The second ISA will be performed when approximately two-thirds of the subjects enrolled (randomized) have had an opportunity to complete the study.

The ISA will involve the descriptive review of deaths, SAEs, discontinuations due to AEs, and discontinuations due to the following 4 events:

1. *An episode of status epilepticus during the 12-week double-blind assessment phase.*
2. *A 28-day seizure rate for all PGTC seizures during the 12-week double-blind assessment phase that is greater than 2-times the maximum 28-day study seizure rate during the baseline phase (a 28-day period is defined as 4 consecutive study weeks).*
3. *An episode of a newly emergent generalized seizure type during the 12-week double-blind assessment phase.*
4. *An increase in the rate or intensity of PGTC or other generalized seizure activity during the 12-week double-blind assessment phase that, according to the investigator, is clinically significant.*

The ISA will not include any analysis for efficacy and therefore no type I error (alpha) spending penalty applies.

An External Data Monitoring Committee (E-DMC) will conduct this unblinded interim safety analysis and provide recommendation to the sponsor. An E-DMC Charter will specify the details of how the safety interim analyses are to be conducted, and how

communications between the sponsor and the E-DMC will take place through open and closed meeting sessions. Additionally, the Charter will address the confidentiality of the interim safety information and appropriate measures will be taken to minimize bias so that the integrity of the study is protected.

3.2. Final Analysis and Unblinding

Blinding codes should only be used for an individual subject and the blind broken only in an emergency situation or when it is critical to guide treatment and care of a given subject for reasons of subject safety. At the initiation of the study, the study site will be instructed on the method for breaking the blind for an individual subject. The method will be either a manual or electronic process. When breaking the blind is required the investigator should contact Pfizer before breaking the blind if possible. When the blinding code is broken for a subject, the reason must be fully documented and entered on the appropriate case report form.

The unblinding for the final analysis will follow standard Pfizer procedures.

4. HYPOTHESES AND DECISION RULES

4.1. Statistical Hypotheses

There will be 2 pair-wise comparisons of interest:

- a) Dose Level 2: pregabalin 10 mg/kg/day (maximum 600 mg/day) - placebo, and*
- b) Dose Level 1: pregabalin 5 mg/kg/day (maximum 300 mg/day) - placebo.*

Each dose of pregabalin will be compared to placebo in a pair-wise manner using a sequential step-wise testing procedure to control for multiplicity of testing such that the experiment-wise type I error rate will not exceed the 5% level of significance.

1) The first step will test the null hypothesis of equal treatment effect of Dose Level 2 vs. placebo at $\alpha=0.05$ 2-sided for the primary endpoint.

$$H_{01}: \mu_{\text{PGB Dose Level 2}} - \mu_{\text{PBO}} = \mathbf{0}$$

$$H_{a1}: \mu_{\text{PGB Dose Level 2}} - \mu_{\text{PBO}} \neq \mathbf{0}$$

2) The second step will test the null hypothesis of equal treatment effect of Dose Level 1 vs. placebo at $\alpha=0.05$ 2-sided for the primary endpoint.

$$H_{02}: \mu_{\text{PGB Dose Level 1}} - \mu_{\text{PBO}} = \mathbf{0}$$

$$H_{a2}: \mu_{\text{PGB Dose Level 1}} - \mu_{\text{PBO}} \neq \mathbf{0}$$

4.2. Statistical Decision Rules

If the null hypothesis (H_{01}) of the first step is rejected, then proceed to the second step (H_{02}), otherwise, accept the null hypothesis of the first step (H_{01}), stop further testing, and claim no treatment effect.

If the null hypothesis of the second step (H_{02}) is rejected, then claim a treatment difference for both dose groups of pregabalin [Dose Level 2: 10 mg/kg/day (maximum 600 mg/day) and Dose Level 1: 5 mg/kg/day (maximum 300 mg/day)] from the placebo group for the primary endpoint only; otherwise accept the null hypothesis of the second step (H_{02}), stop further testing, and claim a treatment difference for only pregabalin Dose Level 2: 10 mg/kg/day (maximum 600 mg/day) from placebo for the primary endpoint only.

5. ANALYSIS SETS

5.1. Full Analysis Set (Intent-to-Treat Population)

The efficacy analyses will be performed on the intent to treat (ITT) population which consists of randomized subjects who took at least 1 dose of investigational product during the double-blind assessment phase, have a baseline value and at least 1 post-baseline efficacy assessment (diary entry).

5.2. 'Per Protocol' Analysis Set (PP Population)

None. Protocol Deviations will be addressed (See [Section 5.6](#)) but no PP analyses are planned.

5.3. Safety Analysis Set

The primary analysis set for safety will be the Safety population which will include randomized subjects who took at least one dose of the investigational product.

5.4. Other Analysis Sets

Not applicable.

5.5. Treatment Misallocations

If a subject was randomized but took incorrect treatment, then they will be reported under their randomized treatment group for the efficacy analyses, but will be reported under the treatment they actually received for all safety analyses.

5.6. Protocol Deviations

The list of protocol deviations will be compiled prior to database closure and study unblinding. All deviations will be reviewed and decisions for handling each of the deviations will be made prior to unblinding of the study.

6. ENDPOINTS AND COVARIATES

6.1. Efficacy Endpoint(s)

For all 28-day log seizure endpoints, the results will be reported as “percent reduction in seizures” relative to placebo. For example, a difference between one of the pregabalin doses and placebo of -0.400 on the log transformed scale for the 28-day seizure rate translates into a 33% reduction in the 28-day seizure rate of the pregabalin group from the placebo group (ie, $100\% \times [\exp(-0.400) - 1] = -33\%$). The “percent reduction in seizures” will be calculated for changes versus placebo on the following statistics: the two-sided 95% confidence intervals, the least square means and their standard errors.

An additional back transformation will be calculated for percent reduction in seizures for each pregabalin treatment group relative to placebo for presentation as follows:

$$100\% \times \frac{[\exp(\text{LSMean(pregabalin)}) - 1] - [\exp(\text{LSMean(placebo)}) - 1]}{\exp(\text{LSMean(placebo)}) - 1}$$

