8.5. Summary of Efficacy Analyses

Endpoint (Key Summary Metrics)	Analysis Set	Statistical Method	Model/ Covariates/ Strata	Missing Data	Interpretation
Log _e 28-day PGTC seizure rate (N, LS Mean Diff/SE)	ITT	ANCOVA	Treatment, region, age strata, baseline seizure rate	Days missing from Seizure Diary will be subtracted from rate calculations	Primary Analysis Note: age strata is protocol defined age strata. Baseline is the log of 28-day PGTC rate at baseline
Key summary statistics will be presented for the Log _e 28-day PGTC seizure rate and for the back transformed “percent reduction in seizures” relative to placebo.					
Log _e 28-day PGTC seizure rate (N, LS Mean Diff/SE) (treatment-by-age p-value)	ITT	ANCOVA	Treatment, region, age group, treatment-by-age group interaction, baseline seizure rate	Days missing from Seizure Diary will be subtracted from rate calculations	Supplemental Analysis Note: age groups are Age < 17 yrs and Age ≥ 17 yrs. Baseline is the log of 28-day PGTC rate at baseline.
Key summary statistics will be presented for the Log _e 28-day PGTC seizure rate and for the back transformed “percent reduction in seizures” relative to placebo.					
Responder rate (%)	ITT	Logistic regression	Treatment, region, age strata	Days missing from Seizure Diary will be subtracted from rate calculations	Secondary Analysis
Proportion Seizure-free days (%)	ITT	ANCOVA	Treatment, region, age strata, baseline	Days missing from Seizure Diary will be subtracted from rate calculations	Exploratory Analysis Each seizure type: PGTC, myoclonic, tonic/tonic, absence, and clonic seizures. Baseline for this endpoint is the proportion of seizure free days at baseline.
Number of seizure-free days gained (N, Mean, SE)	ITT	ANCOVA	Treatment, region, age strata, baseline	Days missing from Seizure Diary will be subtracted from rate calculations	Exploratory Analysis Each seizure type: PGTC, myoclonic, tonic/tonic, absence, and clonic seizures. Baseline for this endpoint is the number of adjusted seizure free days at baseline.

Proportion PGTC Seizure-freedom (%)	ITT	Logistic regression	Treatment, region, age strata	Days missing from Seizure Diary will be subtracted from rate calculations	Exploratory Analysis
Log _e 28-day PGTC seizure rate (N, LS Mean Diff/SE)	ITT	ANCOVA	Treatment, region, age strata, baseline	Multiple imputation will be applied.	Sensitivity Analysis. Baseline is the log of 28-day PGTC rate at baseline.

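### Section 6.1 of the SAP lists standard errors among the statistics to be converted to percent reduction; applied literally, the conversion gives percent-scale standard errors about 1.5 and 1.8 times too large at the planned effects (a reporting error only)

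*SAP*

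**What the plan says.** SAP Section 6.1 introduces percent reduction relative to placebo for all the log-transformed 28-day seizure endpoints. Its worked example turns a log-scale difference of -0.400 into -33% by 100% x [exp(-0.400) - 1]. The next sentence says that the percent reduction "will be calculated for changes versus placebo on the following statistics: the two-sided 95% confidence intervals, the least square means and their standard errors".

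Section 6.1 then adds a second back-transformation, built from the least squares means of a pregabalin arm and the placebo arm. It needs two arm means as input, so it cannot be applied to a standard error and supplies no formula for one.

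Section 8.1 (primary analysis) and Appendix 1 (derivations) show the first conversion for a difference only. Neither gives a formula for a percent-scale standard error.

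In Section 8.5 the primary-analysis row names N and the least squares mean difference with its SE as the key metrics. The note below that row begins "Key summary statistics will be presented for the Log" and goes on to call for both the log-scale rate and its back-transformed percent version. The same note follows the treatment-by-age analysis.

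Section 8.1 builds the test statistics and the two-sided 95% confidence intervals from the log-scale difference and its standard error.

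**The concern.** A difference and its confidence limits are points on the log scale, and a monotone function carries points over correctly. A standard error is a measure of spread. Putting it through 100% x [exp(x) - 1] does not give the standard error of the percent reduction. The result has three visible faults:

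- It ignores the estimate, so two doses with equal log-scale standard errors show the same percent figure whatever their effects.
- It is always positive, and on a scale where reductions are negative it looks like an increase.
- It does not agree with the width of the back-transformed confidence interval printed beside it.

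At stake is one figure in the table that presents the primary result on the percent scale, and in any other table that follows the same rule. A programmer working from the SAP has no other formula to use. Anyone who took the percent-scale standard error at face value would understate the precision of both comparisons.

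**Working it through.** **Inputs, all from the SAP**

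- Planned differences: -0.358 (Dose Level 1) and -0.534 (Dose Level 2), Section 2.2.
- SD: 0.67, since "a smaller standard deviation of 0.67 was used to assess the power and initial sample size requirements"; 0.73 from the meta-analysis; and 0.72, which underlies the cap, described as giving "80% power to detect a treatment difference of -0.358 on the log scale with a standard deviation of 0.72". All are in Section 2.2.
- Subjects per group: 56 planned (Section 2.1), at most 65 after re-estimation (Section 2.2).

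**Step 1. Reproduce the plan's own figures.** 100 x [exp(d) - 1] gives -30.1% at -0.358, -41.4% at -0.534 and -33.0% at -0.400, as stated. Two-sided power at 0.05 with 56 per group, by the normal approximation:

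| Difference | SD | Computed | Table 1 |
|---|---|---|---|
| -0.534 | 0.73 | 0.972 | 0.970 |
| -0.534 | 0.67 | 0.988 | 0.984 |
| -0.358 | 0.73 | 0.737 | 0.742 |
| -0.358 | 0.67 | 0.807 | 0.800 |

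The agreement is close, so SD x sqrt(2/n) is a fair stand-in for the standard error that the plan has in mind.

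**Step 2. Log-scale standard error of a difference.** SE = 0.67 x sqrt(2/56) = 0.1266.

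**Step 3. Section 6.1 applied literally.** 100 x [exp(0.1266) - 1] = 13.5 points. The difference does not enter, so the figure is the same for both doses.

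**Step 4. Approximate standard error on the percent scale (delta method).** 100 x exp(d) x SE:

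- At -0.358: 100 x 0.699 x 0.1266 = 8.85 points; 13.50 / 8.85 = 1.53.
- At -0.534: 100 x 0.586 x 0.1266 = 7.42 points; 13.50 / 7.42 = 1.82.

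**Step 5. Check without the delta method.** The 95% limits at -0.358 are -0.358 ± 1.96 x 0.1266. Back-transformed, they are -45.5% and -10.4%. Their width, 35.1 points, divided by 3.92 is 8.9 points. At -0.534 the limits are -54.3% and -24.9%, which give 7.5 points. Both agree with Step 4 and not with 13.5. The exact lognormal SD gives 8.96 and 7.51 points (ratios 1.51 and 1.80).

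**Step 6. Sensitivity.**

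| n per group | SD | Log SE | Literal rule | Delta, -0.358 (ratio) | Delta, -0.534 (ratio) |
|---|---|---|---|---|---|
| 56 | 0.67 | 0.1266 | 13.50 | 8.85 (1.53) | 7.42 (1.82) |
| 56 | 0.73 | 0.1380 | 14.79 | 9.64 (1.53) | 8.09 (1.83) |
| 65 | 0.67 | 0.1175 | 12.47 | 8.22 (1.52) | 6.89 (1.81) |
| 65 | 0.72 | 0.1263 | 13.46 | 8.83 (1.53) | 7.40 (1.82) |

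The ratio barely moves with SD or n, because it is roughly exp(-d) x (1 + SE/2). It depends mainly on the effect. With SD 0.67 and 56 per group it would be 13.50 / 12.66 = 1.07 at a difference of zero, and it grows as the reduction grows.

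**The case against.** The best defence is that Section 6.1 never writes exp(SE) - 1. Its formula is attached to a difference of -0.400, and the sentence on standard errors could mean only that a standard error should be shown on the percent scale. A careful programmer might then use the delta method unprompted. Section 8.1 and Appendix 1 do not repeat the instruction. This stands in part: the size of the error depends on literal application. But the sentence names standard errors as something the conversion is calculated on, and no other formula appears anywhere. Section 8.5 also makes the SE a key metric and calls for key statistics on both scales.

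The second defence is that little harm follows. This largely stands. Tests and intervals come from the log scale, the back-transformed limits are valid, and Section 8.5 also calls for the log-scale statistics.

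A reader might infer that a clearly significant Dose Level 1 effect would look borderline, because 30.1 / 13.5 = 2.2 while the log-scale ratio is 0.358 / 0.1266 = 2.8. The documents do not support that. A percent change divided by its standard error is not the trial's test under any formula: the delta-method figure gives 30.1 / 8.85 = 3.4, which misses 2.8 in the other direction. At Dose Level 2 it gives 41.4 / 7.42 = 5.6, against 0.534 / 0.1266 = 4.2 on the log scale. Even 2.2 exceeds 1.96.

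Nor does any single percent-scale standard error describe the interval fully, because the interval is asymmetric: at -0.358 it reaches 15.4 points below the estimate and 19.7 above.

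**Conclusion.** The point holds as a reporting error. As written, Section 6.1 leads to a percent-scale figure that is not a standard error of the percent reduction. At the planned effects it is about 1.5 times (Dose Level 1) and 1.8 times (Dose Level 2) too large, across every SD and sample size checked from Section 2.2.

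This rests on three assumptions: the formula is applied literally to the standard error; the log-scale standard error is close to SD x sqrt(2/n); and the observed differences are near the planned ones. Smaller observed effects would give a smaller overstatement.

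A reader might infer that the primary inference is compromised. It is not. The p-values, the step-wise procedure, the confidence intervals on both scales, the point estimates and the sample size are all unaffected. The item is minor, but worth correcting because it changes a number printed beside the primary result.

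**What to change.** - **Section 6.1:** remove standard errors from the list of statistics to be back-transformed, leaving the differences in least squares means and their 95% confidence limits.
- **Section 8.5:** state that the SE is reported on the log scale only, and that precision on the percent scale is given by the back-transformed 95% limits.
- **If a percent-scale standard error is still wanted:** specify 100% x exp(difference) x SE, with the SE on the log scale. Label it approximate and not for testing. This formula belongs to the first back-transformation, not to the additional one built from the two arm means.

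The cost is one phrase in Section 6.1, one sentence in Section 8.5 and one table column. No data, analysis model or test changes.
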